10.0 Data and Specimen Banking*

- 10.1 Data will be recorded on paper forms with identifiers in order to permit resolution of any incomplete/unclear data entries. Data will be deidentified upon transfer to an electronic spreadsheet for analysis. The identifiable data forms will be retained until publication of results in order to permit any supplemental analyses requested by peer reviewers. The deidentified data may be retained indefinitely for potential future use, such as in serving as the underlying dataset for power analysis of a future study.
- 10.2 Deidentified data may be reviewed by the study sponsor. Release of deidentified data may be requested by contacting the PI and/or sponsor. Both the PI and study sponsor must approve release. Release will only be made to personnel who are qualified researchers pursuing legitimate research projects, in the opinion of the PI and/or sponsor. Identifiable data will not be released except as required by law.

11.0 Data Management* and Confidentiality

- 11.1 Data will be summarized by reporting mean (SD) of continuous variables such as BMI and age, percentages for categorical data such as patient sex, and raw count for inadvertent arterial punctures.
- 11.2 As this is an observational study, a power analysis is not useful.
- 11.3 All investigators are CITI- and HIPAA-certified. Completed data collection forms will be maintained in locked cabinets in Anesthesiology department offices, which are a patient-restricted area. As noted in section 10 above, the deidentified data will be retained indefinitely. Only investigators will have access to study data, but they will transmit an electronic copy of deidentified study data to the sponsor upon request. Qualified researchers may request an electronic copy of the deidentified data as listed in section 10 above. Identifiable data will not be released except as required by law.

12.0 Provisions to Monitor the Data to Ensure the Safety of Subjects*

The investigators believe that this is a Minimal Risk study. The only research-related procedure is the inclusion of a small FDA-approved device in the apparatus used to perform CVC placement, in accordance with its labeling.

13.0 Withdrawal of Subjects*

- 13.1 The investigators have not identified any circumstances in which participants would be withdrawn without their consent.
- 13.2 The investigators do not anticipate situations in which advance plans for orderly termination of research participation would be required.
- 13.3 The investigators do not anticipate any requests for withdrawal from the study.

14.0 Risks to Subjects*

- 14.1 Previous studies on this sterile, single-use device have identified no adverse events arising due to its use. The only issue identified to date is the size of the device; a few operators (reported in reference 3 listed above) would prefer that it be smaller. It is therefore possible, but has not ever been demonstrated, that the device's presence may impede CVC placement in some way. This risk is completely reversible, because the device can simply be removed from the needle apparatus if it is in the way. As in any study, there are risks of confidentiality breach. This study does not gather data that are especially sensitive, so the consequences of any confidentiality breach are minor. All risks are mitigated to the extent possible by restricting enrollment to a population that would have received CVC placement regardless of the existence of this study.
- 14.2 The presence of the device in the needle apparatus may present some unforeseeable risk, but as noted above, no such risks have been reported, and the device can simply be removed so that the CVC placement can proceed as usual.
- 14.3 The investigators have not identified any risks to the embryo or fetus should a subject be pregnant at the time of the study.
- 14.4 The investigators have not identified any risks to others who are not subjects.

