1.0 Objectives*

- 1.1 This is a single-arm observational trial of a new FDA-approved device (Compass Vascular Access device, Centurion Medical Products, Williamston MI; formerly Mirador Biomedical). This device is a compact, sterile, single-use extravascular blood pressure transducer with a continuous digital pressure display. This pressure measurement provides an aid in the confirmation of appropriate venous access. The device has FDA 510(k) clearance as substantially equivalent to existing devices on the market. Evidence of this clearance is included with this application.
- 1.2 The investigators plan to enroll 40 consenting patients with $\text{BMI} \geq 35$ who require central venous catheterization for clinical reasons independent of the existence of this study. For purposes of the study, the investigators will record data germane to the procedure as well as operator satisfaction. Analysis of these data will be used to evaluate the appropriateness of the device for this procedure in the obese population, where device ergonomics may be more of a factor than in previous studies.
- 1.3 This study is not investigating the safety of the device, because the primary outcome is operator satisfaction. None of the observed outcomes relate directly to device safety, and the study is not powered to detect rare adverse events.
- 1.4 This study is also not investigating the effectiveness of the device. The investigators are not gathering any data that would permit evaluation of the device's accuracy or precision, which are the salient factors for effectiveness of a measurement device.
- 1.5 Deidentified study data may be shared with the sponsor, but the investigators do not plan to submit study data to the FDA.

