4.0 Study-Wide Number of Subjects*

- 4.1 The planned completed sample size is 40 patients. The investigators request HRRC permission to enroll **up to 45 patients** in order to accommodate any whose CVC procedures may be cancelled between consenting and commencement of the actual procedure, but will only complete data collection for 40 patients.

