8.0 Study Endpoints*

- 8.1 This is an observational study. The main data point of interest is operator satisfaction. The number of inadvertent arterial punctures

identified by the device (if any) will also be recorded. The data collection form is included with this HRRC application.

8.2 The investigators have not identified any safety endpoints.

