9.0 Procedures Involved*

9.1 This is an observational study to be completed on 40 patients meeting the inclusion/exclusion criteria. Subjects presenting for CVC placement at the UNMH operating suites will be prepared as usual and consent obtained. The Compass pressure measurement device will be included in the CVC placement apparatus as per the manufacturer's directions. Data will be recorded on the placement procedure as well as routine patient demographic data. Identifiers will not be recorded.

9.2 A photograph of the device (with attached syringe and needle) is below.

9.3 The only research procedure is the inclusion of the device in the CVC placement apparatus, for patients who would already be having CVC placement regardless of the existence of this study. The research does not modify routine practice surrounding CVC placement (patient selection and preparation, operating personnel, catheter equipment, the procedure itself, or medications used) in any way. These considerations should mitigate risks.

9.4

- As noted above, enrollment of subjects from a population already presenting for CVC placement regardless of the existence of this study mitigates study risks. The investigators are similarly not modifying routine CVC practice except to specify the use of the studied device.
- The project does not specify the use of any drugs. The device being studied is the Compass for CVC pressure transducer device (Centurion Medical Products, Williamston MI).
- The data collection form is included with this application.

9.5 Data to be collected include routine demographic data (age, sex, height, weight, BMI, ASA status), data surrounding the CVC placement procedure (insertion location, use of ultrasound guidance, venous pressure before/after guidewire placement, operator satisfaction), and incidence of inadvertent arterial puncture.

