15.0 Potential Benefits to Subjects*

- 15.1 While rare, inadvertent arterial puncture is possible during CVC placement. The studied device does not eliminate this risk, but rather permits early identification of arterial placement through pressure measurement; pulsatile pressure indicates arterial placement. Identification of arterial puncture at this point, before introduction of the guidewire or catheter, greatly reduces the consequences of arterial puncture. In a previous study on this device (reference 3 above), arterial puncture was identified in 1.7% of subjects, and all were recognized before guidewire insertion (and thus clearly before catheter insertion; no guidewires or catheters were inserted in arteries). Subjects in this study may similarly

receive the benefit of early identification of inadvertent arterial puncture, if any of these punctures do occur.

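### Should the protocol name early removal of the device as a data item, since it foresees that the device may be taken off?

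*Protocol*

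**What the plan says.** Section 1.2 sets the aim: to "evaluate the appropriateness of the device for this procedure in the obese population, where device ergonomics may be more of a factor". Section 8.1 then fixes what is measured: "The main data point of interest is operator satisfaction", together with the number of arterial punctures that the device identifies.

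Section 9.5 lists the procedural items as "insertion location, use of ultrasound guidance, venous pressure before/after guidewire placement, operator satisfaction", plus the incidence of arterial puncture and routine demographics. Section 11.1 plans means with SD, percentages, and a "raw count for inadvertent arterial punctures".

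Removal appears only in the risk section. Section 14.1 calls it possible, though never demonstrated, that the device could hinder placement, and answers that "the device can simply be removed from the needle apparatus if it is in the way". Section 14.2 gives the same answer for unforeseen risks: "the device can simply be removed so that the CVC placement can proceed as usual".

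Section 4.1 allows up to 45 enrolments for 40 completed patients, in order to "accommodate any whose CVC procedures may be cancelled between consenting and commencement of the actual procedure".

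**The concern.** The protocol names the ergonomic difficulty it has in mind and what would happen next, but leaves that event out of every place where it describes the data. Unlike a choice of summary statistic, this cannot be repaired in an analysis plan: if nobody notes at the bedside that the device came off, the fact is lost.

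Two things could be at stake. First, a low satisfaction rating might mean that the operator disliked the size of the device, or that the device was unusable in that patient. These are different messages about its suitability in obese patients. Second, if cases with removal dropped out of the satisfaction summary, the result would look better than it should.

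**Working it through.** The protocol states no removal rate and derives no figure on this point, so there is nothing of its own to reproduce. The check has four parts.

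**1. Does the text exclude recording a removal?**
- 8.1 and 11.1 do not mention it.
- 9.5 does not mention it either, but introduces its list as items that the data include, not as a complete set.
- 1.2 promises data germane to the procedure in addition to satisfaction, and 9.1 says that data on the placement will be recorded. Taking the study device off during placement falls within both.
- 8.1 and 9.4 refer to a data collection form in the application, and 22.6 to a handout for participating physicians. Neither is shown, and a yes/no field with a reason would normally sit on the form.

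The absence is therefore established for the wording of 8.1, 9.5 and 11.1, but not for the study's data capture.

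**2. Can the satisfaction denominator go wrong?**

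Suppose, as an assumption, that about 90% of operators who keep the device on are satisfied and all who remove it are dissatisfied.

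| Removals among 40 | Removed cases left out | All started cases |
|---|---|---|
| 4 | 32/36 = 89% | 32/40 = 80% |
| 8 | 29/32 = 91% | 29/40 = 72.5% |

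The gap is real only if removed cases are left out, and no section says to leave them out. Section 4.1 reserves the 45 − 40 = 5 extra enrolments for procedures cancelled before they begin. A case started with the device attached is not one of those, so it stays among the 40. The plan as written leads to the right-hand column.

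**3. How many removals might there be, and how precisely would 40 patients measure them?**

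With an assumed true rate p, the expected count is 40p and P(at least one) = 1 − (1 − p)^40.

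| Assumed p | Expected count | P(at least one) |
|---|---|---|
| 1% | 0.4 | 33.1% |
| 2% | 0.8 | 55.4% |
| 5% | 2.0 | 87.1% |
| 10% | 4.0 | 98.5% |

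Exact (Clopper-Pearson) 95% intervals with n = 40:

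| Observed | Proportion | 95% interval |
|---|---|---|
| 0 | 0% | 0 to 8.8% |
| 1 | 2.5% | 0.1% to 13.2% |
| 2 | 5.0% | 0.6% to 16.9% |
| 4 | 10.0% | 2.8% to 23.7% |

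For scale, section 15.1 reports that in an earlier study "arterial puncture was identified in 1.7% of subjects". This agrees with section 2.0, where 5/298 = 1.68%. At 1.7%, 40 × 0.017 = 0.68 punctures are expected, and P(none) = 0.983^40 = 50.4%. The puncture count is thus also likely to be zero or very small, but that says nothing about how often the device would be removed.

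**4. Would a simple removal field measure the right thing?**

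Section 2.0 describes needle, then guidewire, then catheter, with the device between syringe and needle and a channel for the guidewire. On that description the device appears to come away with the needle before the catheter goes in. This is an inference; the protocol does not say so. If it is right, a field asking whether the device was removed before the end of placement would be answered yes in all 40 cases. Only unplanned removal, with its reason, would be informative. Even that is not purely ergonomic, because 14.2 also foresees removal for an unforeseen risk.

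**The case for a change.** The strongest argument for a change is that this is data capture at the bedside, not analysis. The protocol foresees the event twice, its rationale is ergonomics, and one field would cost almost nothing. If the form has no such field, no later document can restore the information. A blank pressure after guidewire placement would hint at removal but would give neither its step nor its reason. Section 10.1 keeps forms with identifiers so that unclear entries can be resolved, but 9.1 says that identifiers will not be recorded, so that route deserves limited weight.

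Much of this stands. The three sections do not name removal, and knowing about it would help in reading low ratings. Two steps go too far. It is not shown that the item is missing from the form. Nor is it shown that ratings could not be told apart without it, since neither the satisfaction scale nor any comment space is visible. To call removal the most direct sign of poor ergonomics is a judgement, because 14.2 allows other reasons.

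**Conclusion.** No change to the plan follows. The protocol makes no false statement here and does not contradict itself: 14.1 and 14.2 explain why a hypothetical hindrance is reversible, and they do not define an outcome. Followed as written, the study collects its stated main outcome in every started procedure and leaves room to record procedural events such as removal. What remains is a gap in detail that the form, or an investigator noting an obvious event in a placement of about 15 minutes, can sensibly fill.

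The possible gain is one descriptive count that helps in reading low ratings. At assumed rates of 1% to 10% it would be expected to lie between 0.4 and 4 in 40, and 4 of 40 would still have an interval from 2.8% to 23.7%. The protocol sets no hypothesis or threshold that such a count would test.

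The conclusion rests on three assumptions: that 9.5 is an open list, as worded; that started cases count among the 40, as the reason given in 4.1 implies; and that the unseen form is at least as broad as 1.2 and 9.1 promise. If the form proved to have no place for unplanned removal, adding one would be a reasonable courtesy to readers, but not the correction of an error.

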15.0 Potential Benefits to Subjects*

- 15.1 While rare, inadvertent arterial puncture is possible during CVC placement. The studied device does not eliminate this risk, but rather permits early identification of arterial placement through pressure measurement; pulsatile pressure indicates arterial placement. Identification of arterial puncture at this point, before introduction of the guidewire or catheter, greatly reduces the consequences of arterial puncture. In a previous study on this device (reference 3 above), arterial puncture was identified in 1.7% of subjects, and all were recognized before guidewire insertion (and thus clearly before catheter insertion; no guidewires or catheters were inserted in arteries). Subjects in this study may similarly

receive the benefit of early identification of inadvertent arterial puncture, if any of these punctures do occur.

16.0 Vulnerable Populations*

16.1 This project does not involve the commonly-recognized vulnerable populations.

17.0 Community-Based Participatory Research*

This study does not constitute community-based participatory research.

18.0 Sharing of Results with Subjects*

18.1 This study does not involve testing or other results that may affect future treatment decisions for subjects, so there are none to share with subjects. Final study results will also not be shared with patients, because others' experience has no direct effect on the patient.

19.0 Setting

19.1 Research activities will occur at the UNMH operating suites and in the Anesthesiology department offices.

- Subjects will be identified from among the patient population at the UNMH operating suites. CVC placement for recruited patients will occur as planned at the UNMH main operative setting.

20.0 Resources Available

20.1 All investigators who will perform the CVC placements are licensed physicians authorized to practice and perform this procedure at UNMH. Investigator [name] PhD is a staff member in the Department of Anesthesiology with experience in study design and data analysis.

20.2 Describe other resources available to conduct the research: For example, as appropriate:

- A conservative estimate of the number of patients presenting to the UNMH main OR suites who require CVC placement is 10-20 per week. Of these, approximately 1/3 have BMI ≥ 35 .
- Investigators will conduct study activities in conjunction with their routine clinical and non-clinical duties.
- The operating suites at UNMH are equipped with the personnel, facilities, and other resources needed to place CVCs and respond to any eventuality arising from the placement of a CVC.
- Upon HRRC approval, the approved version of the protocol will be distributed to all participating investigators. The

investigators do not anticipate any need for protocol modifications after HRRC approval.

21.0 Prior Approvals

- 21.1 Beyond the routine departmental review process and HRRC review, no other approvals are necessary for this project.

22.0 Recruitment Methods

- 22.1 After HRRC approval, enrollment will occur among at least 40 and up to 45 patients meeting the inclusion/exclusion criteria.
- 22.2 Subjects will be drawn from adult patients requiring CVC placement at the UNMH main operating rooms.
- 22.3 Investigators will identify subjects from among their routine patients.
- 22.4 No patient recruitment materials will be used.
- 22.5 Subjects will not be paid.
- 22.6 Investigators have drafted a proposed information handout for participating physicians who will place CVCs with the Compass device in this study. The handout notes that an investigator will obtain patient consent, and outlines both the target population and the study procedures. It also encourages participating physicians to contact the PI with any remaining questions.

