7.0 Study Timelines*

- 7.1 Describe:
 - A given individual will participate in the study for approximately 15 minutes, representing the time required for the CVC placement.
 - The investigators anticipate that the study sample can be enrolled in approximately six months to one year.
 - The investigators estimate that all analyses will be completed in one year after completion of enrollment.

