27.0 Consent Process

- 27.1. Consent will be obtained by an HRRC-approved investigator prior to the commencement of research procedures. All investigators are CITI- and HIPAA-certified.

- 27.1.1. The consent process will occur in the UNMH operating suites.

- 27.1.2. Coercion and undue influence will be avoided by not paying participants, and by assuring prospective enrollees that their participation is entirely voluntary: they can still receive CVC placement without participating.
- 27.1.3. Additional lead time for prospective subjects to consider participation is not available in this study because CVC placement is usually performed shortly after the decision that one is needed. Similarly, there is published research that examines the effect of additional consideration time on patients' views of the consent process and their rights in anesthesia clinical trials. This research has shown that consent on the day of surgery for trials of treatments with similar risks/benefits does **not** compromise patient rights or welfare. The study authors (Murphy et al., "Consent for Anesthesia Clinical Trials on the Day of Surgery," *Anesthesiology* 2016; 124:1246-55) found that anesthesia patients approached for research consent on the day of surgery were **satisfied with the consent process**, felt that the protocol was **well explained and comprehended**, and agreed that **the setting was appropriate**. Conversely, these patients strongly disagreed that they were anxious at the time of consent, felt any obligation to participate, or regretted participating. Importantly, **these results were not changed by the use of a preadmission telephone call** to describe the research protocol and provide greatly extended time for patients to consider their participation. If patients felt that day-of-surgery consent represented a violation of their rights or an imposition on their welfare, these results would have been very different.
- 27.1.4. As this study involves a one-time clinical procedure, the investigators believe that a one-time consent procedure is appropriate, and the study thus does not require provisions for ensuring ongoing consent.

Subjects not fluent in English

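### Section 22.3 leaves the choice of which eligible patients to approach to investigators, with no visible order of approach or tally, in a single-arm study whose primary outcome is a subjective operator rating

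*Protocol*

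**What the plan says.** Section 5.0 of the Protocol refers the reader to section 22 for local recruitment. There, 22.2 gives the source: "Subjects will be drawn from adult patients requiring CVC placement at the UNMH main operating rooms". Section 22.3 gives the method in one sentence: "Investigators will identify subjects from among their routine patients". Section 3.1 gives eligibility, and 4.1 sets 40 completed patients with up to 45 enrolled.

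On who does what, 20.1 states: "All investigators who will perform the CVC placements are licensed physicians authorized to practice and perform this procedure at UNMH". Section 22.6 adds that participating physicians who place lines receive a handout that "outlines both the target population and the study procedures", and that an investigator takes consent. The handout and the data collection form (8.1) are cited but not shown.

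On flow, 20.2 puts the number of main-OR patients needing a line at "10-20 per week. Of these, approximately 1/3 have BMI" of 35 or more, and 7.1 says: "The investigators anticipate that the study sample can be enrolled in approximately six months to one year". On working conditions, 20.2 says "Investigators will conduct study activities in conjunction with their routine clinical and non-clinical duties", and 27.1.3 explains that "CVC placement is usually performed shortly after the decision that one is needed".

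Sections 1.3 and 8.1 make operator satisfaction the main outcome. Section 1.2 says what the data are for: judging whether the device is suitable in obese patients, where ergonomics may matter more than in previous studies.

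**The concern.** The outcome is an opinion, there is one arm, and the person who decides whether to approach a patient may also be the person who later rates the device. With no comparator drawn from the same patients, any effect of how patients were chosen goes straight into the reported satisfaction.

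The study exists because the device's ergonomics may be a problem in larger patients, and 14.1 allows that the device might get in the way. If placements expected to be awkward were passed over, the study would under-sample the situation it was set up to examine. The opposite is also possible: difficult cases might be sought out because they are the interesting ones. Nothing visible would let a reader tell which happened, or whether either did.

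This cannot be repaired at analysis. Who is approached is settled at recruitment, and patients who were never approached leave no record.

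**Working it through.** **1. Is there a rule or a count anywhere in the visible text?**

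- Section 22 names who identifies subjects (22.3), from where (22.2) and how many (22.1). It gives no consecutive, random or other order of approach.
- Section 9.3 says that routine patient selection is unchanged. That concerns who receives a central line, not which eligible patients are asked to join the study.
- Section 9.5 lists BMI, ASA status, insertion location, ultrasound use, pressures, satisfaction and arterial puncture. These describe enrolled patients only. No eligible, approached or declined count is listed.
- The handout (22.6) and data form (8.1) are not shown and could hold either.

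**2. Can the chooser be the rater?** By 20.1 some investigators place lines, so the roles can coincide. By 22.6 participating physicians place lines while an investigator takes consent, so the roles can also be separate. The Protocol does not say how often either applies.

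**3. How much room for choice is there?** The target of 40 has no derivation to reproduce: 11.2 declines a power analysis, and no precision target is given. What can be computed is patient flow.

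Inputs: 10 to 20 patients a week and a share of about 1/3 (20.2); six months to one year, taken as 26 to 52 weeks (7.1); 40 completed (4.1).

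Weekly flow with BMI of 35 or more = weekly volume × 1/3:
- 10 × 1/3 = 3.33
- 20 × 1/3 = 6.67

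Pool during anticipated enrolment = weekly flow × weeks:

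| Volume per week | 26 weeks | 52 weeks |
|---|---|---|
| 10 | 3.33 × 26 = 86.7 | 3.33 × 52 = 173.3 |
| 20 | 6.67 × 26 = 173.3 | 6.67 × 52 = 346.7 |

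So the pool is roughly 87 to 347. Forty completed patients are 40/86.7 = 46% of the smallest pool and 40/346.7 = 12% of the largest.

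**4. What the pool does not measure.** It covers all main-OR patients above the BMI limit, not the investigators' own patients, whose share is not stated. It is not reduced for the 3.1 exclusions or for refusals, whose rates are not given. In the other direction, 20.2 calls its volume estimate conservative. The window is an anticipated duration, not a fixed one. If every patient in the flow were enrolled, 40 would be reached in 40/6.67 = 6 to 40/3.33 = 12 weeks.

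**The case against.** The strongest reply is that nothing here is wrong on its face. Sections 22.2, 22.3 and 3.1 do not conflict. The Protocol describes a case series, disclaims safety and effectiveness (1.3, 1.4) and plans only descriptive summaries (11.1). Convenience enrolment is ordinary in such work, and 9.5 records enough to describe who was enrolled. Much of this stands: there is no contradiction, and the point is an improvement rather than an error. It does not remove the point, because 1.2 goes beyond description to a judgement about the obese population, and the 9.5 data cannot show who was passed over or why.

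A second reply concerns the flow figures. A reader might infer from 40 out of 87 to 347 that investigators will be picking patients. The documents do not support that. Data collection stops at 40, so a surplus of reachable patients could simply mean an earlier finish. Work alongside routine duties (20.2), short lead time (27.1.3), exclusions and refusals may explain much of the gap. Nor can one infer a share of the pool below which no choice would remain: investigators with few eligible patients could still pass some over and take longer. This reply stands in full, and the figures are context only.

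A third reading would be that operators choose the cases on which they rate the device. Section 22.6 does not allow this as a general statement, since chooser and rater may be different people.

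Finally, the handout or data form may already contain a rule or log. That possibility stays open.

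**Conclusion.** The point holds as a cheap improvement of low severity, with medium confidence. Section 22.3 leaves the choice of whom to approach to investigators, some of whom may also rate the device, and the visible text neither orders that choice nor records it. With a subjective primary outcome and a single arm, this leaves the ratings open to being unrepresentative of the obese patients they are meant to speak for.

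No bias has been shown, and neither its size nor its direction can be computed from the documents. The conclusion rests on two assumptions: that the unseen handout and data form contain no rule or log, and that at least some investigators will both identify patients and rate the device, or otherwise use discretion in whom to approach. The matter belongs in the Protocol rather than a statistical analysis plan, because it governs recruitment.

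**What to change.** Amend 22.3 to say that every eligible patient under a participating investigator's care is approached consecutively whenever an investigator is available to consent, until 40 are completed. Keep a short de-identified tally, limited to those patients, of eligible, approached, declined and completed. Where the HRRC permits, add a coarse reason for each eligible patient not approached, such as no investigator available, too little time or operator's choice, with the last counted as a departure from the rule. If the handout or data form already contains such a rule or log, cite it in 22.3 instead.

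The consecutive rule is the main remedy. The availability clause keeps some discretion, which is realistic given the working conditions in 20.2 and 27.1.3. The tally shows how often the rule was not followed, but a count alone cannot show whether the missed patients were harder cases.

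The cost is a sentence in 22.3, a small logging burden and slightly less flexibility in recruitment. No extra patients are needed, and the target of 40 does not change.
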